5.1.2.3. Baseline

Unless specified otherwise, for the purpose of analyses involving change from baseline during treatment with rFVIIIIFc, baseline is defined as the last non-missing measurement (that can be used for data analysis i.e. was not taken during a surgical/rehabilitation period) taken prior to the first dose of study medication rFVIIIIFc.

If a patient requires rescreening during the study, then baseline characteristics for the summary table will be taken from the first screening visit.

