9.5. Vital Signs

Vital signs include temperature, pulse, systolic and diastolic blood pressure, respiratory rate, pulse, temperature, height and weight. All vital signs except height and weight were measured prior to and approximately 20 minutes after each dose of rFVIII Fc. Height and weight were measured prior to dosing. Temperature was measured using the following methods: oral, rectal, tympanic, forehead, and axillary.

Vital signs will be summarized for the observed values and change from baseline using descriptive statistics for the Safety Analysis Set. Temperature measurements not taken by the same method pre and post dose will be excluded from the analysis with the exception of the combination of tympanic and rectal measurements. Evaluations taken during major surgical/rehabilitation periods will not be included in any summary.

A listing of all vital signs will be provided, including from unscheduled visits and during surgical/rehabilitation periods. Vital signs collected during surgical/rehabilitation periods as well as those occurring on the day of surgery will be flagged in this listing.

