Summary of shifts from baseline to minimum/maximum post-baseline value for laboratory results: Hematology
Summary of potentially clinically significant laboratory abnormalities: Hematology
Summary of laboratory results and change from baseline for episodic and prophylactic regimens: Blood Chemistry
Summary of laboratory results and change from baseline for ITI regimen: Blood Chemistry
Shifts from baseline to minimum/maximum post-baseline value for laboratory results: Blood Chemistry

	Statistical Analysis Plan	Final v1.0
---	----------------------------------	-------------------

Summary of shifts from baseline to minimum/maximum post-baseline value for laboratory results: Blood Chemistry
Summary of potentially clinically significant laboratory abnormalities: Blood Chemistry
Inhibitors
Summary of inhibitor development by Nijmegen-modified Bethesda assay
Summary of peak titer inhibitor development by Nijmegen-modified Bethesda assay
Summary of time to inhibitor development
Other Safety
Summary of anti-rFVIII Fc antibodies
Summary of vital sign results and change from baseline for episodic and prophylactic regimens
Summary of vital sign results and change from baseline for ITI regimen

List of listings

Background/demography
Listing of lot numbers for study drug
Listing of protocol versions consented to
Listing of end of study disposition
Listing of demographic and baseline characteristics
Listing of caregiver’s demography
Listing of medical and surgical history
Listing of informed consent date and analysis populations
Listing of hemophilia history – diagnosis and diagnostic factors
Listing of Hemophilia history – bleeding history 3 months prior to screening
Listing of hemophilia history – pre-study FVIII treatment
Listing of risk factors
Listing of prior and concomitant medication taken through the end of study visit
Listing of concomitant medication taken after the end of study visit and prior to follow-up
Listing of maternal concomitant medication taken through the end of study visit
Listing of maternal concomitant medication taken after the end of study visit and prior to follow-up
Listing of other therapy or concomitant procedures
Listing of major and minor protocol deviations
Exposure/dosing
Listing of all injections and treated bleeding episodes
Listing of injections to treat a bleed
Listing of exposure
Listing of dose and consumption endpoints
Listing of prescribed dose and regimen changes
Listing of compliance endpoints
Efficacy

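### SAP 9.5 matches thermometer method before and after each dose, but the planned summary is change from the pre-first-dose baseline, where no method match is required

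*SAP*

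**What the plan says.** SAP 9.5 describes when the readings are taken: "All vital signs except height and weight were measured prior to and approximately 20 minutes after each dose of rFVIII Fc". It lists five ways of taking temperature: "Temperature was measured using the following methods: oral, rectal, tympanic, forehead, and axillary".

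It then states the planned analysis: "Vital signs will be summarized for the observed values and change from baseline using descriptive statistics for the Safety Analysis Set". The next sentence is the exclusion rule: "Temperature measurements not taken by the same method pre and post dose will be excluded from the analysis". That sentence makes a single exemption, for tympanic paired with rectal readings. The same section provides a listing of all vital signs.

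Section 9.5 gives no baseline of its own, so SAP 5.1.2.3 applies: "baseline is defined as the last non-missing measurement" that is usable for analysis and "taken prior to the first dose of study medication rFVIIIIFc".

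The table list in SAP section 12 has two vital-sign tables. One is the "Summary of vital sign results and change from baseline for episodic and prophylactic regimens"; the other is the equivalent for the ITI regimen. Neither 9.5 nor the table list plans a pre-dose to post-dose difference within a visit.

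**The concern.** By excluding mixed-method pairs and exempting only one combination, the SAP itself treats most of the five methods as non-interchangeable. A rule of that kind should protect the difference that is tabulated. Here the rule compares the two readings around a dose, while the tabulated difference is between a later reading and one reading taken before the first dose.

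Two errors can follow. A change that mixes methods enters the summary without any check. And readings are removed that could have been used, both for change from baseline and in the observed-value summary, where no pairing is needed.

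The study is single-arm (SAP 3.1.2), so no control group would show the same artefact. The children are under 6 years at consent (Protocol 8.1), and participation can last up to about 3 years (Protocol 7.3), so a change of method during follow-up is plausible. Protocol 16.5.2.3 planned counts of subjects with abnormal vital signs, but the SAP table list has no such table. The two tables above are therefore the only tabulation of temperature as a vital sign.

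**Working it through.** The plan gives no figure on this point, so the check is logical: which pair the rule compares, which pair the analysis compares, and where the two differ.

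**Inputs**
- Methods: five (SAP 9.5).
- Rule: keep a visit's readings if the pre-dose and post-dose methods agree, counting tympanic and rectal as agreeing (SAP 9.5).
- Analysis: observed values, and later value minus baseline (SAP 9.5 and section 12).
- Baseline: last usable value before the first dose (SAP 5.1.2.3).

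**Examples at a visit after the first dose**

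| Baseline | Pre-dose | Post-dose | SAP rule | Compared with baseline |
|---|---|---|---|---|
| rectal | axillary | axillary | kept | both changes cross methods |
| axillary | axillary | oral | excluded | pre-dose value matches, yet is lost |
| rectal | rectal | tympanic | kept under the exception | consistent, if the exception is accepted |

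**All combinations of baseline, pre-dose and post-dose method**
- Total: 5 × 5 × 5 = 125.
- Pre/post pairs the rule keeps: 5 identical + 2 orderings of tympanic and rectal = 7. Over 5 baselines, 7 × 5 = 35 are retained.
- Excluded: 125 − 35 = 90.
- Retained and consistent with baseline, honouring the exception: oral, forehead and axillary baselines give 1 each; rectal and tympanic baselines give 4 each. That is 3 × 1 + 2 × 4 = 11.
- Retained but crossing methods relative to baseline: 35 − 11 = 24. If tympanic and rectal count as different, only 5 of the 35 are consistent and 30 cross.
- Excluded although at least one reading matches the baseline method: 8 for each of oral, forehead and axillary, and 12 for each of rectal and tympanic. That is 3 × 8 + 2 × 12 = 48 of the 90 (36 under strict matching).

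These are counts of possible combinations. They show that both errors can occur under the rule, not how often they would occur.

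**Where the rule does work.** If the pre-dose value at the first-dose visit is the baseline, the pair the rule checks is the pair the analysis uses, and 0 retained combinations cross methods. The problem concerns later visits.

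**Where the rule is silent.** Protocol 4.2.2.1 says clinic dosing takes place only if warranted. A visit without a dose has no pre/post pair, so the rule does not say what happens to its temperature reading.

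**With matching to baseline instead.** Of the 24 cross-method combinations now retained, 0 would contribute a cross-method change. In 48 of the 90 now excluded, at least one reading would become usable for change from baseline.

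**The case against.** The strongest objection is that the exclusion sentence directly follows the mention of change from baseline. Pre and post dose could then mean the reading before the first dose against any later reading, which would remove the mismatch. This cannot be ruled out, but it is less likely: the same paragraph has just used the before-and-after language for each dose. If it was the intent, the sentence still needs rewording, because a programmer could reasonably implement the within-visit check.

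A second objection is that the SAP excludes such readings from the analysis without saying whether that covers observed values, changes or both. That is fair. On the plain words it covers both, and the text should say.

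A third is that little depends on this. That stands: it is one vital sign in a descriptive table, with no hypothesis test.

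Four stronger readings are tempting and the documents do not support them:
- **A sizeable spurious mean change in temperature.** The mean shift is the sum, over method switches, of the share of children making that switch times its offset. The documents give neither quantity. Nor do they show that switches run in one direction; with mixed directions the shift could be near zero.
- **Long follow-up makes switching common.** Three years is the upper end; Protocol 7.3 gives about 6 months to 3 years. At the 3- to 5-day prophylaxis intervals in Protocol 10.2.3, 50 exposure days take 50 × 3 = 150 to 50 × 5 = 250 days, or about two to three 12-weekly visits. A preceding episodic phase or ITI lengthens this.
- **A post-dose fever could vanish.** An excluded reading leaves only the summary. It stays in the full listing (SAP 9.5), and an untoward fever falls under the adverse-event definition in SAP 9.3.
- **24 of 35 or 48 of 90 as error rates.** They count possible combinations and are not frequencies.

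**Conclusion.** The point holds as a mismatch between a stated rule and the analysis it is meant to protect. On the natural reading of SAP 9.5 with 5.1.2.3, the method check guards a difference that is never tabulated and leaves the tabulated one unguarded. At visits after the first dose, cross-method changes can stay in, and readings that match the baseline method can be dropped from the summaries.

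The conclusion rests on two assumptions: that pre and post dose refers to each dose, and that a child's method can differ between baseline and a later visit. The SAP's own list of five methods allows the second but does not show how often it happens, so the size cannot be determined.

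The consequence is limited to the descriptive temperature summary. Inhibitor development, efficacy and adverse-event reporting are not affected. This is a minor correction, worth making because it is cheap.

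**What to change.** In SAP 9.5, replace the exclusion sentence with:

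*Change from baseline in temperature is calculated only when the baseline and the post-baseline value were taken by the same method (tympanic and rectal treated as the same method, if that exception is kept); all observed temperatures are included in the observed-value summary.*

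This settles which pair must match, says what happens to observed values, and covers visits without a clinic dose. No separate rule for within-visit differences is needed, because none are planned.

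The text change is small, and the method has to be known already for the existing rule to be applied. The cost is that fewer patients contribute to temperature change at later visits, so the number contributing should be shown at each visit. The observed-value summary will pool methods. Splitting it by method is possible, but with five methods, several visits and regimens, and about 105 children, many cells would be sparse.

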9.6. Physical Examination Findings

All physical examination abnormalities with body system will be listed by patient and visit.

	Statistical Analysis Plan	Final v1.0
---	----------------------------------	-------------------

10. CHANGES TO PLANNED ANALYSIS

This SAP is based on Version 6 of the approved study protocol dated 12 February 2018. The major differences in the analysis described in this SAP compared to the protocol are:

- The Full Analysis Set consists of all patients who received at least 1 dose of rFVIIIIFc and were enrolled.
- An ITI Analysis Set and period was defined for the analysis of immune tolerance induction response data.
- The health outcomes questionnaire used in the study is not as specified in the protocol. The analysis described refers to that which was actually used and this can be found in [Appendix A](#)

12. LIST OF TABLES, LISTINGS, AND FIGURES

List of tables

Background/Demography
Summary of disposition by treatment regimen
Summary of disposition by inhibitor subgroup
Summary of disposition by inhibitor sub-classification I
Summary of enrollment by country and site by treatment regimen
Summary of patients attending key study visits
Summary of patients attending key ITI study visits
Summary of demographics and baseline characteristics by treatment regimen
Summary of demographics and baseline characteristics by inhibitor subgroup
Summary of demographics and baseline characteristics by inhibitor sub-classification
Summary of medical and surgical history by treatment regimen
Summary of hemophilia history by treatment regimen
Summary of bleeding history in the 3 months prior to study entry by treatment regimen
Summary of risk factors by inhibitor subgroup
Summary of physical examination at screening by treatment regimen
Summary of prior medications by treatment regimen
Summary of concomitant medications by treatment regimen
Summary of major protocol deviations by treatment regimen
Exposure/Dosing
Summary of injections and days of exposure to rFVIII Fc by treatment regimen
Summary of injections and days of exposure to rFVIII Fc by inhibitor subgroup
Summary of injections and days of exposure to rFVIII Fc by inhibitor sub-classification
Summary of injections and days of exposure to rFVIII Fc by EPD entry compliance by treatment regimen
Summary of duration of dosing with rFVIII Fc by treatment regimen
Summary of duration of dosing with rFVIII Fc by inhibitor subgroup
Summary of duration of dosing with rFVIII Fc by inhibitor sub-classification
Summary of duration of dosing with rFVIII Fc by EPD entry compliance by treatment regimen
Summary of prophylactic dose IU/kg
Summary of ITI dose IU/kg
Summary of prophylactic dosing interval
Summary of ITI dosing interval
Summary of annualized rFVIII Fc consumption (IU/kg) by treatment regimen
Summary of annualized rFVIII Fc consumption (IU/kg) by inhibitor subgroup
Summary of annualized rFVIII Fc consumption (IU/kg) by inhibitor sub-classification
Summary of last prescribed prophylactic dose and dosing frequency
Summary of compliance for the treatment of bleeding episodes by treatment regimen
Summary of prophylactic and ITI dose compliance

	Statistical Analysis Plan	Final v1.0
---	----------------------------------	-------------------

Summary of prophylactic and ITI dosing interval compliance
Summary of prophylactic and ITI compliance
Summary of EPD entry compliance by treatment regimen
Efficacy
Summary of bleeding episodes by treatment regimen
Summary of bleeding episodes by inhibitor subgroup
Summary of bleeding episodes by inhibitor sub-classification
Summary of annualized bleeding rates by treatment regimen
Summary of annualized bleeding rates by inhibitor subgroup
Summary of annualized bleeding rates by inhibitor sub-classification
Summary of annualized bleeding rate by type of bleed and treatment regimen
Summary of annualized bleeding rates by type of bleed and inhibitor subgroup
Summary of annualized bleeding rates by type of bleed and inhibitor sub-classification
Summary of annualized bleeding rate by location of bleed and treatment regimen
Summary of annualized bleeding rates by location of bleed and inhibitor subgroup
Summary of annualized bleeding rates by location of bleed and inhibitor sub-classification
Summary of annualized bleeding rate by location, type of bleed and treatment regimen
Summary of annualized bleeding rates by location, type of bleed and inhibitor subgroup
Summary of annualized bleeding rates by location, type of bleed and inhibitor sub-classification
Summary of annualized bleeding rate by history of bleeding (estimated frequency of bleeds in prior 3 months) by treatment regimen
Summary of annualized bleeding rate - patients with no major protocol deviations potentially impacting efficacy by treatment regimen
Summary of patient's assessment of response to rFVIII Fc injections for the treatment of bleeding episodes by treatment regimen
Summary of patient's assessment of response to rFVIII Fc injections for the treatment of bleeding episodes by compliance to treat the bleed and treatment regimen
Summary of number of injections required for resolution of a bleeding episode by treatment regimen
Summary of number of injections required for resolution of a bleeding episode by inhibitor subgroup
Summary of number of injections required for resolution of a bleeding episode by inhibitor sub-classification
Summary of dose (IU/kg) of rFVIII Fc for resolution of bleeds by treatment regimen
Summary of dose (IU/kg) of rFVIII Fc for resolution of bleeds by inhibitor subgroup
Summary of dose (IU/kg) of rFVIII Fc for resolution of bleeds by inhibitor sub-classification
Summary of physician's global assessment of the response for episodic and prophylactic regimens
Summary of physician's global assessment of the response for ITI regimens
Summary of health outcomes for episodic and prophylactic regimens
Summary of incremental recovery (IR) (IU/dL per IU/kg) for episodic and prophylactic regimens
ITI

	Statistical Analysis Plan	Final v1.0
---	----------------------------------	-------------------

Summary of ITI response and relapse
Surgery
Investigators'/surgeons' assessment of patients' hemostatic response to rFVIIIFc post surgery
Number of injections and dose required to maintain hemostasis during major surgery
Estimated total blood loss during major surgery
Total rFVIIIFc consumption (IU/kg) per major surgery
Summary of number of bleeds after surgery per major surgery
Adverse events
Overall summary of rFVIIIFc treatment-emergent adverse events by treatment regimen
Overall summary of rFVIIIFc treatment-emergent adverse events by inhibitor subgroup
Overall summary of rFVIIIFc treatment-emergent adverse events by inhibitor sub-classification
Overall summary of rFVIIIFc treatment-emergent adverse events by treatment regimen and EPD entry compliance
Summary of rFVIIIFc treatment-emergent adverse events by treatment regimen
Summary of rFVIIIFc treatment-emergent adverse events by inhibitor subgroup
Summary of rFVIIIFc treatment-emergent adverse events by inhibitor sub-classification
Summary of rFVIIIFc treatment-emergent adverse events by treatment regimen and EPD entry compliance
Summary of rFVIIIFc treatment-emergent adverse events by treatment regimen and preferred term in descending order of incidence
Summary of rFVIIIFc treatment-emergent serious adverse events by treatment regimen
Summary of rFVIIIFc treatment-emergent adverse events by severity and treatment regimen
Summary of rFVIIIFc treatment-emergent adverse events by relationship to treatment and treatment regimen
Summary of severe rFVIIIFc treatment-emergent adverse events by treatment regimen and preferred term in descending order of incidence
Summary of rFVIIIFc treatment-emergent adverse events leading to treatment discontinuation or withdrawal by treatment regimen
Routine laboratory
Summary of laboratory results and change from baseline for episodic and prophylactic regimens: Hematology
Summary of laboratory results and change from baseline for ITI regimen: Hematology
Shifts from baseline to minimum/maximum post-baseline value for laboratory results: Hematology
Summary of shifts from baseline to minimum/maximum post-baseline value for laboratory results: Hematology
Summary of potentially clinically significant laboratory abnormalities: Hematology
Summary of laboratory results and change from baseline for episodic and prophylactic regimens: Blood Chemistry
Summary of laboratory results and change from baseline for ITI regimen: Blood Chemistry
Shifts from baseline to minimum/maximum post-baseline value for laboratory results: Blood Chemistry

	Statistical Analysis Plan	Final v1.0
---	----------------------------------	-------------------

Summary of shifts from baseline to minimum/maximum post-baseline value for laboratory results: Blood Chemistry
Summary of potentially clinically significant laboratory abnormalities: Blood Chemistry
Inhibitors
Summary of inhibitor development by Nijmegen-modified Bethesda assay
Summary of peak titer inhibitor development by Nijmegen-modified Bethesda assay
Summary of time to inhibitor development
Other Safety
Summary of anti-rFVIII Fc antibodies
Summary of vital sign results and change from baseline for episodic and prophylactic regimens
Summary of vital sign results and change from baseline for ITI regimen

List of listings

Background/demography
Listing of lot numbers for study drug
Listing of protocol versions consented to
Listing of end of study disposition
Listing of demographic and baseline characteristics
Listing of caregiver’s demography
Listing of medical and surgical history
Listing of informed consent date and analysis populations
Listing of hemophilia history – diagnosis and diagnostic factors
Listing of Hemophilia history – bleeding history 3 months prior to screening
Listing of hemophilia history – pre-study FVIII treatment
Listing of risk factors
Listing of prior and concomitant medication taken through the end of study visit
Listing of concomitant medication taken after the end of study visit and prior to follow-up
Listing of maternal concomitant medication taken through the end of study visit
Listing of maternal concomitant medication taken after the end of study visit and prior to follow-up
Listing of other therapy or concomitant procedures
Listing of major and minor protocol deviations
Exposure/dosing
Listing of all injections and treated bleeding episodes
Listing of injections to treat a bleed
Listing of exposure
Listing of dose and consumption endpoints
Listing of prescribed dose and regimen changes
Listing of compliance endpoints
Efficacy
Listing of the number of bleeding episodes during the efficacy period

	Statistical Analysis Plan	Final v1.0
---	----------------------------------	-------------------

Listing of derived bleeding endpoints based on individual bleeding episodes
Listing of derived bleeding and injection endpoints based on patients
Listing of the Investigator’s classification of bleeding episodes which differed from the caregiver’s classification
Listing of Investigator’s assessment of patient’s response to rFVIII Fc injections for the treatment of bleeding episodes
Listing of the by-patient summary of the assessment of response to rFVIII Fc for the treatment of bleeding episodes
Listing of physician’s assessment of the patient’s global response to his treatment regimen
Listing of health outcomes
Listing of FVIII activity levels
Listing of incremental recovery
ITI
Listing of patients on ITI
Surgery
Listing of major surgery information – hospitalization data
Listing of major surgery information – blood loss
Listing of major surgery information – dosing during and for the first 14 days post surgery
Listing of major surgery information – transfusions and surgeon’s assessment of hemostatic response to rFVIII Fc
Listing of injections and bleeding episodes during and for the first 14 days following major surgery
Listing of minor surgery information – hospitalization data
Listing of minor surgery information – blood loss
Listing of minor surgery information – dosing during and on the day of surgery
Listing of minor surgery information – transfusions and surgeon’s assessment of hemostatic response to rFVIII Fc
Adverse events
Listing of adverse events
Listing of serious adverse events
Listing of related adverse events
Listing of adverse events leading to discontinuation of treatment and/or the study
Listing of adverse events during the surgical/rehabilitation periods
Listing of deaths
Routine laboratory
Listing of laboratory normal ranges
Listing of laboratory values: Hematology
Listing of abnormal laboratory values based on the normal range: Hematology
Listing of abnormal laboratory values based on potentially clinically significant abnormalities: Hematology
Listing of laboratory values: Blood Chemistry
Listing of abnormal laboratory values based on the normal range: Blood Chemistry

	Statistical Analysis Plan	Final v1.0
---	----------------------------------	-------------------

Listing of abnormal laboratory values based potentially clinically significant abnormalities: Blood Chemistry
Inhibitors
Listing of laboratory values: Inhibitor results
Listing of abnormal laboratory values: Inhibitor results
Listing of inhibitor patients who achieve remission without ITI
Listing of inhibitor patients
Other safety
Listing of laboratory values: Anti-rFVIII Fc antibodies
Listing of abnormal laboratory values: Anti-rFVIII Fc antibodies
Listing of vital sign measurements
Listing of abnormal findings from physical examination
Listing of weight

List of figures

Safety
Kaplan-Meier plot of incidence of inhibitor development by exposure days and titer

[Redacted text block containing multiple paragraphs of blacked-out content]

[REDACTED]

[REDACTED]

[REDACTED]

[REDACTED]

[REDACTED]

[REDACTED]

[figure not shown]
[figure not shown]
[REDACTED]

To: TMF – 997HA306

Re: Quality Memo to Regarding SAP for 997HA306

This memo is to document that V1.0 of this Statistical Analysis Plan is March 30, 2018 and the original date on the cover sheet which was approved was erroneously recorded as April 30, 2018. This date has been corrected, initialed and dated by the author on the final version of the document which is filed in this TMF.

The SAP was effective upon approval on 03 Apr 2018.

Quality Memo Completed By:	
Signature: 	Date: 17 APR 2018
